4.1 Screening Data, Eligibility and Recruitment

The total number of screened patients and reasons for not entering the trial will be summarised and presented. A CONSORT flow diagram (appendix A) will be used to summarise the number of patients who were:

- assessed for eligibility at screening
- eligible at screening
- ineligible at screening*
- eligible and randomised
- eligible but not randomised*
- received the randomised allocation
- did not receive the randomised allocation*
- lost to follow-up*
- completed intervention and assessments
- completed assessments but not intervention
- withdrew consent*
- discontinued the intervention*
- randomised and included in the primary analysis
- randomised and excluded from the primary analysis*

*reasons will be provided.

4.2 Baseline Patient Characteristics

Baseline characteristics of intervention group stratified by treatment allocation (Atorvastatin-Placebo vs. Placebo-Atorvastatin) will be tabulated, using descriptive statistics for continuous variables, and number and percentages of patients for categorical variables. There will be no statistical analysis of treatment difference. Any clinically important imbalance between the treatment groups will be noted.

The patient demographics and baseline characteristics to be summarised include study center (Drammen/Vestfold), previous atorvastatin discontinuation (yes/no), age in years, gender, education (high, low), living alone (yes/no), lipid lowering treatment (yes/no, type, high-intensity therapy, low-intensity therapy, total number of statins used), coronary index diagnosis (myocardial infarction vs. stable/unstable CHD), >1 coronary event prior to the index event, comorbidities (heart failure, hypertension, diabetes, stroke/TIA, rheumatic or inflammatory disease, arthrosis, hypo or

STATISTICAL ANALYSIS PLAN for MUScle Side-Effects of atorvastatin in coronary patients (MUSE) – a randomized controlled trial

hyperthyroidism), concomitant medication used regularly (total number of drugs, potentially interacting drugs, and analgesics, coronary risk factors (LDL-C, smoking status, physical activity, BMI, hsCRP), other laboratory tests (estimated GFR, creatinine kinase, alanine aminotransferase), consulted primary care physician regarding statin side-effects (yes/no).

5 Outcome Definitions

5.1 General Definitions and Derived Variables

5.1.1 Muscular symptom intensity

Individual mean difference in muscular symptom intensity = Mean muscular symptom intensity (regardless of characteristics and location) reported by the patient the last three weeks during the treatment period on atorvastatin – the last three weeks during the treatment period on placebo. The last consecutive three weeks completed during each treatment period will be used in patients who discontinue due to intolerable muscle symptoms.

Muscular symptom intensity is reported through a 0-10 cm Visual Analogue Scale (VAS) in a patient diary delivered at study start. The patients are asked to also report muscular symptom intensity on a 0-10 Likert scale. Results from the VAS scale will be replaced by the results from the Likert scale in case of missing data on the VAS scale.

VAS scores over the last 3 weeks in each treatment period have been chosen as primary end-point for three reasons: i) to ensure steady state concentrations of atorvastatin; ii) to maximize the likelihood for the symptoms reported to being truly related to the current (and not previous) treatment period; iii) the duration of the treatment period being sufficiently long to produce SAMS (>3 weeks). VAS score has also been chosen as primary outcome in two previous SAMS studies^{16,17}.

5.1.2 The proportion of patients who report muscle symptoms on atorvastatin treatment compared with on placebo (dichotomous SAMS classification)

The proportion of patients who report muscle symptoms on atorvastatin treatment and not on placebo (dichotomous SAMS classification). A 25% intra-individual change in the VAS symptom score has been regarded clinically relevant in a previous validation study of the scale¹⁴. As previously described it has been reported as the smallest change in VAS symptom score corresponding to ‘a little more’ or ‘a little less’ symptoms was 1.3 cm, with a lower limit of the CI at 1.0 cm in a previous study by Gallagher et al¹⁴. Accordingly, confirmed SAMS will be defined as a 25% higher individual VAS score during the treatment period on atorvastatin vs. placebo and ≥ 1.0 cm absolute difference.

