1.1 Background and rationale

Statin non-adherence (i.e. patients not taking their prescribed drugs) remains a major public health concern in cardiovascular disease patients, leading to adverse outcomes in terms of morbidity, mortality and healthcare costs¹⁻³. The principal reason for statin non-adherence and discontinuation is statin-associated muscle symptoms (SAMS)⁴. SAMS, comprising a heterogeneous group of muscle symptoms including pain/aching, stiffness, tenderness or cramps, usually with normal or minimally elevated creatinine kinase levels, is prevalent challenge in clinical practice⁴. In contrast, serious statin side-effects, including liver failure, rhabdomyolysis, or myositis with elevated creatinine kinase levels in blood, are very rare^{4,5}. In randomized trials, statin therapy appears to cause only a slightly increased risk of side-effects of 1-5% compared with placebo, far below the prevalence reported in clinical practice, amounting to 30% in observational studies^{6,7}. Strict entry criteria in the randomized statin trials, excluding patients with polypharmacy, multiple comorbidities, elderly, females and low body weight, factors that predispose to musculoskeletal symptoms, may in part explain the diverging frequency of SAMS⁴. A major limitation of observational studies is a lack of blinding. Patients on statins may expect to experience side-effects, and therefore report a higher percentage than in a comparable population not on statins, the so-called 'nocebo' effect. Two previous studies, in subjects without cardiovascular disease, has tested whether SAMS reported by the patients are related the statin therapy⁸⁻⁹. In a randomized, double-blind crossover study that included patients complaining of SAMS at study start, only 36% experienced that their muscle symptoms persisted during treatment with simvastatin 20 mg and disappeared during placebo treatment⁸. Accordingly, SAMS was confirmed to be related to the statin treatment in one-third of the patients. The proportion of CHD patients with confirmed SAMS, treated with potent statins recommended for these patients, remains unknown. Furthermore, the clinical presentation (i.e. location, intensity and characteristics) of the muscle symptoms in CHD patients with and without confirmed SAMS remains to be investigated.

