2.3 Sample size

Sample size calculations are based on our being able to detect a 1 cm difference in the VAS symptom score between the treatment periods on atorvastatin and placebo since the smallest change in VAS symptom score corresponding to ‘a little more’ or ‘a little less’ symptoms was 1.3 cm, with a lower limit of the CI at 1 cm in a previous study by Gallagher et al¹⁴. Gallagher et al. report a standard

STATISTICAL ANALYSIS PLAN for MUScle Side-Effects of atorvastatin in coronary patients (MUSE) – a randomized controlled trial

deviation (SD) of 1.7 for a difference of 1.0 between two VAS symptom scores. Because of the differences in both populations and specific VAS scale between that study in this one, we use SD=2.5 to account for a much larger variation in this study. With n=68, we will have 90% power to detect a difference of 1.0, using a one-sample T test. With n=68, we will also have 80% power to detect a difference of 40% SAMS under statins vs. 15% SAMS under placebo, using the McNemar test for paired probabilities. To account for some missing information due to drop-outs or and protocol deviations, we plan to include 80 patients.

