5.3 Secondary Outcomes Definitions

5.3.1 Dichotomous SAMS classification

The proportion of patients with confirmed SAMS, as defined in Section 5.1.2, where the mean of the symptoms scores in the last three weeks of each treatment period is used.

5.3.2 Relationship between muscle symptom intensity and atorvastatin and metabolites level in blood

The correlation between individual differences in mean muscular symptom intensity and atorvastatin and metabolites in blood plasma among patients with confirmed SAMS, as defined in Section 5.1.2. The 20 variables in Table 1 will be used.

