6.4.1 Dichotomous SAMS classification

The proportion of patients with confirmed SAMS will be estimated as the number of patients with confirmed SAMS divided by the total number of patients in the full analysis set. A 95% confidence interval for the proportion will be estimated with the Wilson score confidence interval²⁰.

6.4.2 Relationship between muscle symptom intensity and atorvastatin and metabolites level in blood

The correlations between differences in muscular symptom intensity and levels of atorvastatin and metabolites among patients with confirmed SAMS will be estimated with Spearman rank correlation coefficients, with 95% confidence intervals estimated by the Bonett-Wright approximation²¹. In addition, scatter plots and linear regression analyses may be used to illustrate the associations.

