6.4.3 Diagnostic properties of atorvastatin and metabolites for classification of confirmed SAMS

Methods for analysis of ROC curves and measures of diagnostic accuracy will be used to identify cut-off values of metabolite concentrations that can discriminate between confirmed SAMS and non-SAMS. These methods include calculating sensitivity, specificity, and area under the ROC curve (with 95% confidence intervals).

STATISTICAL ANALYSIS PLAN for MUScle Side-Effects of atorvastatin in coronary patients (MUSE) – a randomized controlled trial

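### The confirmed-SAMS share is reported without a placebo-side comparator, although its rule would label roughly 20% to 34% of patients if atorvastatin had no effect

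*SAP*

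**What the plan says.** Section 5.1.2 (and the footnote to section 1.2.2) sets two criteria that must both hold: "confirmed SAMS will be defined as a 25% higher individual VAS score during the treatment period" on atorvastatin compared with placebo, and an absolute difference of at least 1.0 cm. Section 5.3.1 fixes the inputs: "the mean of the symptoms scores in the last three weeks of each treatment period is used". Each patient therefore contributes one atorvastatin-placebo pair.

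Section 6.4.1 divides the number labelled by the size of the full analysis set and adds: "A 95% confidence interval for the proportion will be estimated with the Wilson score confidence interval". It gives no figure for patients who are worse on placebo. Yet the first secondary objective in section 1.2.2 is a comparison with placebo, and section 2.3 gives power for a paired McNemar comparison of 40% against 15%. No such comparison appears in section 6.

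On variability, section 2.3 cites a VAS validation study with a standard "deviation (SD) of 1.7 for a difference of 1.0 between two VAS symptom scores" and then states: "we use SD=2.5 to account for a much larger variation in this study".

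The label is reused in sections 6.4.2 (correlations), 6.4.3 (ROC analysis, seeking "cut-off values of metabolite concentrations that can discriminate between confirmed SAMS and non-SAMS"), 6.4.5 (non-SAMS against controls), 6.4.7 and 6.4.8 (symptom location and characteristics), 6.4.9 (time to confirmed SAMS) and 6.4.10 (genotypes). The SAP does not mention that the label may be met by chance.

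**The concern.** A 1.0 cm threshold is only 1.0/2.5 = 0.4 of the SD that the SAP plans for. A single pair of period means will often differ by that much in either direction without any drug effect. The Wilson interval is valid for the share meeting the rule, but it describes sampling error only. It does not show how much of that share would arise on an inert tablet.

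A reader of the headline proportion may take it as the fraction of patients whose symptoms are caused by atorvastatin. The label is also the reference standard or grouping variable for the metabolite, symptom and genotype analyses, so chance labels carry over into those results.

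**Working it through.** **Inputs from the SAP.** Threshold 1.0 cm and 25% (5.1.2); one pair of three-week means (5.3.1); SD 2.5 for planning and 1.7 cited (2.3); n = 68 (2.3); two-sided alpha 0.05 (2.4.2); scale 0-10 cm (5.1.1). **Assumed, because the SAP does not give them:** mean VAS 2 to 6 cm, between-patient SD 1 to 2 cm, normal scores cut off at 0 and 10.

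**Step 1: what the SD of 2.5 refers to.** For a one-sample t test with difference 1.0, SD 2.5 and n = 68, the noncentrality is (1.0/2.5) × √68 = 3.30 and the power is 90.2%. This reproduces the stated 90%, and 68 is the smallest n that reaches it. So 2.5 is the SD of the individual atorvastatin-minus-placebo difference D.

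**Step 2: 1 cm criterion alone, no drug effect.** P(D ≥ 1.0) = 1 − Φ(1.0/SD).
- SD 2.5: 1 − Φ(0.400) = 34.5%
- SD 1.7: 1 − Φ(0.588) = 27.8%
- SD 1.0 (assumed, for range): 1 − Φ(1.0) = 15.9%

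**Step 3: both criteria and the scale limits, no drug effect.** The 25% criterion adds something only when 0.25 × placebo score exceeds 1.0 cm, that is, when the placebo score is above 4 cm. Simulated over the assumed means and between-patient SDs:

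| SD of D | 1 cm alone | Both criteria, SD set before cutting at 0 and 10 | Both criteria, SD matched after cutting |
|---|---|---|---|
| 2.5 | 34.5% | 28-33% | 29-34% |
| 1.7 | 27.8% | 20-27% | 21-28% |

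In 68 patients, 20% to 34% is about 14 to 23 people. A null result of 23/68 would be reported as 33.8%, Wilson 95% CI 23.7% to 45.7%.

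**Step 4: the mirror-image share.** With no effect, D is symmetric about zero, so the same share should meet the reversed rule (placebo at least 25% and 1.0 cm higher). In the simulations the two shares agreed to about 0.2 percentage points. Their difference is then centred on zero, whatever the SD.

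**Step 5: what the difference measures under an effect.** Suppose every patient is shifted by the planned 1.0 cm at SD 2.5 (1 cm criterion alone). Then P(D ≥ 1) = 50%, P(D ≤ −1) = Φ(−2/2.5) = 21.2%, and the net excess is 28.8 points although all patients are affected. The difference is evidence of an excess and does not count responders.

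**Step 6: the planned paired test.** For McNemar with 40% against 15%, n = 68 and no patient positive in both periods, the discordant shares are 0.40 and 0.15. Then z = (0.25√68 − 1.96√0.55)/√(0.55 − 0.25²) = 0.87, a power of about 81%, which agrees with the stated 80%. The mirror-image pair has this structure, since no patient can meet both rules. Under independence the asymptotic power would be 90%.

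**The case against.** The strongest reply concerns size. The SAP chose 2.5 as a deliberately generous planning value. It gives no repeat-measurement SD for three-week means, and averaging may make the true within-patient SD smaller. Part of the 2.5 may also be real variation in drug response, which would lower the SD under no effect. This stands: the label's actual error rate is unknown and a third is the upper end. It does not remove the point, because at the cited 1.7 the null share is still about 20-27% and the SAP offers no benchmark against which to judge it.

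It can also be said that the Wilson interval is correct for the quantity defined, and that section 2.4.1 makes everything except the primary analysis supportive or exploratory. Both are true. The defect is a missing comparator and the interpretation it invites; the interval itself is not wrong.

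A reader might infer three stronger things that the SAP does not support:
- *That the trial cannot tell a one-third response rate from none.* Section 6.3 tests the mean VAS difference without the label, with 90% stated power for 1.0 cm. Only the proportion taken alone has this limit.
- *That a null share near a third undermines the earlier cross-over result in section 1.1* ("SAMS was confirmed to be related to the statin treatment in one-third of the patients"). That study used a different rule: symptoms that persisted on simvastatin and disappeared on placebo. The closeness of the numbers carries no weight.
- *That the loss of diagnostic accuracy in section 6.4.3 can be stated as a number.* That would need a responder share, a noise SD, a true AUC and an assumption about how label errors relate to metabolite levels. The SAP gives none of these.

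**Conclusion.** The point holds in a limited form. The confirmed-SAMS share in section 6.4.1 is reported without the placebo comparison that the objective names and section 2.3 powered. With no drug effect the rule would still label roughly 20% to 34% of patients. The upper end rests on the planning SD of 2.5, the lower end on SD 1.7, both with the scale assumptions given above; a smaller true within-patient SD would lower the range. The raw share alone cannot be read as the proportion with statin-caused symptoms, and analyses that use the label inherit an unquantified error. The primary analysis is unaffected. This should be changed, but it does not threaten the trial's main conclusion.

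**What to change.** - **Section 6.4.1 (and 5.1.2):** state that the raw share is not the proportion with statin-caused symptoms. Beside it, report the mirror-image share, defined as placebo at least 25% and 1.0 cm higher than atorvastatin on the same three-week means. Give the paired difference between the two shares with a 95% CI and a McNemar-type test. Base the conclusion on that difference and call it a net excess, not the responder share.
- **Section 6.4.3:** state that the label is an imperfect reference and that AUC, sensitivity and specificity are measured against that label.
- **Sections 6.4.2, 6.4.5 and 6.4.7 to 6.4.10:** add the same caveat wherever the label selects or splits patients.

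The cost is a few lines of text and no new data. The headline becomes less favourable and less precise. With 23 of 68 on each side, for example, the difference has an approximate half-width of 1.96 × √((46/68)/68) = 19.5 points, against about 11 points for the Wilson interval on one share.

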5.1.3 Atorvastatin and metabolites level in blood

In the MUSE study design paper¹³, we have described that “atorvastatin and metabolites levels in white blood cells (i.e. lymphocytes) is also a relevant candidate marker for SAMS in addition to plasma”. Importantly, only plasma levels of atorvastatin and metabolites will be determined and related to SAMS in the main study. A separate paper will determine the relationship between SAMS and statin and metabolites level in lymphocytes.

STATISTICAL ANALYSIS PLAN for MUScle Side-Effects of atorvastatin in coronary patients (MUSE) – a randomized controlled trial

Table 1 shows an overview of the different combinations of parent drug (atorvastatin) and metabolites that will be related to SAMS in the study. We expect the variables in bold to be the ones most likely to be related to SAMS.

Table 1. Parent drug and metabolites of ATV to be determined.

Variables	Abbreviations
Atorvastatin acid C0	AA C0
2-OH-atorvastatin acid C0	2OH-AA C0
4-OH-atorvastatin acid C0	4OH-AA C0
Atorvastatin lactone C0	AL C0
2-OH-atorvastatin lactone C0	2OH-AL C0
4-OH-atorvastatin lactone C0	4OH-AL C0
Sum acids C0	Sum A C0
Sum lactones C0	Sum L C0
Sum acids and lactones C0	Sum A+L C0
Atorvastatin acylglucuronide C0	AAG C0
Atorvastatin acid C2	AA C2
2-OH-atorvastatin acid C2	2OH-AA C2
4-OH-atorvastatin acid C2	4OH-AA C2
Atorvastatin lactone C2	AL C2
2-OH-atorvastatin lactone C2	2OH-AL C2
4-OH-atorvastatin lactone C2	4OH-AL C2
Sum acids C2	Sum A C2
Sum lactones C2	Sum L C2
Sum acids and lactones C2	Sum A+L C2
Atorvastatin acylglucuronide C2	AAG C2

5.1.4 Muscular symptom location

Muscular symptom location is obtained through patient self-report measured with the Brief Pain Inventory at the end of each 7-weeks treatment period. Presence of symptoms (yes/no) are noted on the following locations: neck/shoulder/trunk, proximal upper extremities, proximal lower extremities, distal upper extremities, distal lower extremities and bilateral vs. unilateral.

Detailed differences in muscle symptom location (i.e. «Dermatome pain map» (Margoli Dermatome Pain Map) Margolis RB et. Al. Pain 24:57–65, 1986) will be explored in a separate sub-study publication.

STATISTICAL ANALYSIS PLAN for MUScle Side-Effects of atorvastatin in coronary patients (MUSE) – a randomized controlled trial

5.1.5 Muscular symptom characteristics

Muscle symptom characteristics are obtained through patient self-report measured with McGill Pain Questionnaire administrated at the end of each 7-weeks treatment period. Fifteen different characteristics are rated from none (0 points) to strong (3 points).

5.2 Primary Outcome Definition

The primary outcome is the difference between the VAS symptom scores for the mean of the last three weeks of the atorvastatin period and the mean of the last three weeks of the placebo period.

5.3 Secondary Outcomes Definitions

5.3.1 Dichotomous SAMS classification

The proportion of patients with confirmed SAMS, as defined in Section 5.1.2, where the mean of the symptoms scores in the last three weeks of each treatment period is used.

5.3.2 Relationship between muscle symptom intensity and atorvastatin and metabolites level in blood

The correlation between individual differences in mean muscular symptom intensity and atorvastatin and metabolites in blood plasma among patients with confirmed SAMS, as defined in Section 5.1.2. The 20 variables in Table 1 will be used.

5.3.3 Diagnostic properties of atorvastatin and metabolites for classification of confirmed SAMS

Sensitivity, specificity, and area under the ROC curve of blood concentrations of parent drug and the metabolites of atorvastatin for the classification of confirmed SAMS, as defined in Section 5.1.2. The 20 variables in Table 1 will be used.

5.3.4 Statin (ATV) adherence

Statin adherence determined with pill counts in returned tablet boxes and atorvastatin plus metabolites concentration in blood, as defined in Section 3.2.1.

5.3.5 Atorvastatin and metabolites level in patients with failing placebo-test for connecting SAMS to atorvastatin and the control group without muscle symptoms

Difference between levels of atorvastatin and its metabolites in blood plasma at the end of the treatment period with atorvastatin for patients with failing placebo-test for connecting SAMS to atorvastatin (i.e. non-SAMS) and the control group without muscle symptoms. The 20 variables in Table 1 will be used.

5.3.6 Study safety

- Proportion of patients with new-onset CHD symptoms (e.g. angina, dyspnoea)
- Intolerable muscle symptoms leading to discontinuation from the treatment arm
- Proportion of patients with creatine kinase (CK) > 10 times upper limit of the normal range or alaninaminotransferase (ALT) > 3 times upper limit of the normal range in blood

STATISTICAL ANALYSIS PLAN for MUScle Side-Effects of atorvastatin in coronary patients (MUSE) – a randomized controlled trial

- Proportion of patients with serious adverse events (SAEs) and Suspected Unexpected Serious Adverse Reactions (SUSARS).

5.3.7 Muscle symptom location

We define an outcome that is the difference between the presence (yes=1, no=0) of muscle symptoms during atorvastatin treatment and the presence (yes=1, no=0) of muscle symptoms during placebo treatment for each of the following locations:

- neck/shoulder/ trunk
- proximal upper extremities
- proximal lower extremities
- distal upper extremities
- distal lower extremities
- Bilateral vs. unilateral

The outcomes (differences) have three possible values:

- -1, indicating that there are more symptoms on placebo
- 0, indicating that there are equal symptoms on atorvastatin and placebo
- 1, indicating that there are more symptoms on atorvastatin

In addition, we define an outcome that is the difference between the total number of muscle locations marked during atorvastatin treatment and the total number of muscle locations marked during placebo treatment.

